 Local Site Enrollment # of Subjects	 Revised and/or New Study Documents or Subject Materials (e.g. diaries, questionnaires)
 Total Enrollment # of Subjects (Multi-Center Trials)	 Investigator Brochure, Date/Version:
 Change in subject selection or subject population	 Change in Remuneration
 Change of Sponsor/Funding	 Research Related Use of Medical Records
 Study Status Change (i.e., CTE, hold, re-open to enrollment)	 Use of Specimens
 Industry Sponsored Protocols only: Sponsor Amendment/Version #:	 Research Related Use of Discarded Material
 Change related to pharmacy or study drug administration	 Revised Sponsor Protocol, Issue Date/Version:
 Addition/Removal of Co-Investigator or Research Staff Member	
For amendments limited to only the addition or removal of research staff in addition to this form the following is required:	

• Research Staffing Form (1 clean, 1 highlighted)• Revised Part E if amendment involves change in Authorized Prescribers for study medication• Part Q and CITI training documentation for any non-BIDMC research staff member.	

AMENDMENT ATTACHMENTS:

 Revised Sponsor Protocol (New Version) (1 clean, 1 highlighted)
 New or Revised Advertisement (1 clean, 1 highlighted)
 Revised Part A (1 clean, 1 highlighted)
 Revised Part B (1 clean, 1 highlighted)
 Revised Consent Form (1 clean, 1 highlighted)
 Revised Research Participant Materials or Questionnaires (1 clean, 1 highlighted)
 Revised Research Staffing Form (1 Clean, 1 highlighted:)
 Part Q(s) for addition of any non-BIDMC personnel
 Revised/New Part E (Obtain pharmacy signature and detail change below)
 Other Revised Part/Form Document (1 Clean, 1 highlighted:)
Specify:

AMENDMENT DESCRIPTION- REQUIRED FOR ALL SUBMISSIONS

AMENDMENT DETAILS

Indicate which components(s) or element(s) of your protocol are being changed. Check all applicable items.	
 Principal Investigator	 Change and/or New Recruitment or Publicity Materials
 DSMB Reports/Monitoring Reports/Safety Reports	 Recruitment, Publicity Materials and/or procedures
 Revised and/or New Consent Form	 Consent Procedures
 Change and/or Addition of Study Procedures	 Duration of Subject Participation
 Local Site Enrollment # of Subjects	 Revised and/or New Study Documents or Subject Materials (e.g. diaries, questionnaires)
 Total Enrollment # of Subjects (Multi-Center Trials)	 Investigator Brochure, Date/Version:
 Change in subject selection or subject population	 Change in Remuneration
 Change of Sponsor/Funding	 Research Related Use of Medical Records
 Study Status Change (i.e., CTE, hold, re-open to enrollment)	 Use of Specimens
 Industry Sponsored Protocols only: Sponsor Amendment/Version #:	 Research Related Use of Discarded Material
 Change related to pharmacy or study drug administration	 Revised Sponsor Protocol, Issue Date/Version:
 Addition/Removal of Co-Investigator or Research Staff Member	
For amendments limited to only the addition or removal of research staff in addition to this form the following is required:	

• Research Staffing Form (1 clean, 1 highlighted)• Revised Part E if amendment involves change in Authorized Prescribers for study medication• Part Q and CITI training documentation for any non-BIDMC research staff member.	

AMENDMENT ATTACHMENTS:

 Revised Sponsor Protocol (New Version) (1 clean, 1 highlighted)
 New or Revised Advertisement (1 clean, 1 highlighted)
 Revised Part A (1 clean, 1 highlighted)
 Revised Part B (1 clean, 1 highlighted)
 Revised Consent Form (1 clean, 1 highlighted)
 Revised Research Participant Materials or Questionnaires (1 clean, 1 highlighted)
 Revised Research Staffing Form (1 Clean, 1 highlighted:)
 Part Q(s) for addition of any non-BIDMC personnel
 Revised/New Part E (Obtain pharmacy signature and detail change below)
 Other Revised Part/Form Document (1 Clean, 1 highlighted:)
Specify:

AMENDMENT DESCRIPTION- REQUIRED FOR ALL SUBMISSIONS

A detailed description of the amendment, in your own words, **MUST** be provided below. The PI may provide a summary of a lengthy sponsor amendment in an attached cover letter or memo, however this should not simply be a copy of the sponsors amendment and/or letter. Either list the current item followed by the new item, or attach a redlined version of the changed document. If the consent form is revised, attach one copy of the consent form in which the changes (including additions and deletions) are clearly highlighted, and one clean copy of the consent form.

Update study staff.

PI Memo/Cover Letter Describing Changes is attached Sponsor Letter Describing Changes is Attached

Impact on Budget/Funding

Does this amendment affect the current budget for the study?
 
 No
 
 Yes, if yes, explain
 
and contact:
 
 - Clinical Trials Office for Industry Funded Studies - Office of Sponsored Programs for Other Funding Sources 	
Does this amendment affect the current funding for the study?
 
 No
 
 Yes, if yes, explain
 
and contact:
 
 - Clinical Trials Office for Industry Funded Studies - Office of Sponsored Programs for Other Funding Sources
---	--

AMENDMENT RATIONALE- REQUIRED FOR ALL SUBMISSIONS

The reason or justification for the changes **must** be discussed as well as how the change might affect the risk/benefit ratio. Please also address how or if a change in the risk/benefit ratio impacts the informed consent form, and if the change necessitates a change in the consent form. The rationale may be provided **here** or in an attached cover letter or memo.


For amendments limited to only the addition or removal of research staff in addition to this form the following is required:
 
 • Research Staffing Form (1 clean, 1 highlighted) • Revised Part E if amendment involves change in Authorized Prescribers for study medication • Part Q and CITI training documentation for any non-BIDMC research staff member. 	

AMENDMENT ATTACHMENTS:

 Revised Sponsor Protocol (New Version) (1 clean, 1 highlighted)
 New or Revised Advertisement (1 clean, 1 highlighted)
 Revised Part A (1 clean, 1 highlighted)
 Revised Part B (1 clean, 1 highlighted)
 Revised Consent Form (1 clean, 1 highlighted)
 Revised Research Participant Materials or Questionnaires (1 clean, 1 highlighted)
 Revised Research Staffing Form (1 Clean, 1 highlighted:)
 Part Q(s) for addition of any non-BIDMC personnel
 Revised/New Part E (Obtain pharmacy signature and detail change below)
 Other Revised Part/Form Document (1 Clean, 1 highlighted:)
Specify: Lahey Clinic, Inc. Institutional Review Board approval letter. (dated 04/03/2018)

AMENDMENT DESCRIPTION- REQUIRED FOR ALL SUBMISSIONS

A detailed description of the amendment, in your own words, **MUST** be provided below. The PI may provide a summary of a lengthy sponsor amendment in an attached cover letter or memo, however this should not simply be a copy of the sponsors amendment and/or letter. Either list the current item followed by the new item, or attach a redlined version of the changed document. If the consent form is revised, attach one copy of the consent form in which the changes (including additions and deletions) are clearly highlighted, and one clean copy of the consent form.

Participating study site – Local IRB approval granted to Lahey Hospital & Medical Center study site: The CCI approved the addition of Lahey Hospital & Medical Center as a study site on 11/28/2017. Local IRB approval has been obtained at Lahey Hospital & Medical Center; we are submitting a copy of the Lahey Clinic, Inc. Institutional Review Board approval letter.

PI Memo/Cover Letter Describing Changes is attached Sponsor Letter Describing Changes is Attached

Impact on Budget/Funding

 Change and/or Addition of Study Procedures	 Duration of Subject Participation
 Local Site Enrollment # of Subjects	 Revised and/or New Study Documents or Subject Materials (e.g. diaries, questionnaires)
 Total Enrollment # of Subjects (Multi-Center Trials)	 Investigator Brochure, Date/Version:
 Change in subject selection or subject population	 Change in Remuneration
 Change of Sponsor/Funding	 Research Related Use of Medical Records
 Study Status Change (i.e., CTE, hold, re-open to enrollment)	 Use of Specimens
 Industry Sponsored Protocols only: Sponsor Amendment/Version #:	 Research Related Use of Discarded Material
 Change related to pharmacy or study drug administration	 Revised Sponsor Protocol, Issue Date/Version:
 Addition/Removal of Co-Investigator or Research Staff Member	
For amendments limited to only the addition or removal of research staff in addition to this form the following is required:	

• Research Staffing Form (1 clean, 1 highlighted)• Revised Part E if amendment involves change in Authorized Prescribers for study medication• Part Q and CITI training documentation for any non-BIDMC research staff member.	

AMENDMENT ATTACHMENTS:

 Revised Sponsor Protocol (New Version) (1 clean, 1 highlighted)
 New or Revised Advertisement (1 clean, 1 highlighted)
 Revised Part A (1 clean, 1 highlighted)
 Revised Part B (1 clean, 1 highlighted)
 Revised Consent Form (1 clean, 1 highlighted)
 Revised Research Participant Materials or Questionnaires (1 clean, 1 highlighted)
 Revised Research Staffing Form (1 Clean, 1 highlighted:)
 Part Q(s) for addition of any non-BIDMC personnel
 Revised/New Part E (Obtain pharmacy signature and detail change below)
 Other Revised Part/Form Document (1 Clean, 1 highlighted:)
Specify:

 DSMB Reports/Monitoring Reports/Safety Reports	 Recruitment, Publicity Materials and/or procedures
 Revised and/or New Consent Form	 Consent Procedures
 Change and/or Addition of Study Procedures	 Duration of Subject Participation
 Local Site Enrollment # of Subjects	 Revised and/or New Study Documents or Subject Materials (e.g. diaries, questionnaires)
 Total Enrollment # of Subjects (Multi-Center Trials)	 Investigator Brochure, Date/Version:
 Change in subject selection or subject population	 Change in Remuneration
 Change of Sponsor/Funding	 Research Related Use of Medical Records
 Study Status Change (i.e., CTE, hold, re-open to enrollment)	 Use of Specimens
 Industry Sponsored Protocols only: Sponsor Amendment/Version #:	 Research Related Use of Discarded Material
 Change related to pharmacy or study drug administration	 Revised Sponsor Protocol, Issue Date/Version:
 Addition/Removal of Co-Investigator or Research Staff Member	

For amendments limited to only the addition or removal of research staff in addition to this form the following is required:

- Research Staffing Form (1 clean, 1 highlighted)
- Revised Part E if amendment involves change in Authorized Prescribers for study medication
- Part Q and CITI training documentation for any non-BIDMC research staff member.

AMENDMENT ATTACHMENTS:

 Revised Sponsor Protocol (New Version) (1 clean, 1 highlighted)
 New or Revised Advertisement (1 clean, 1 highlighted)
 Revised Part A (1 clean, 1 highlighted)
 Revised Part B (1 clean, 1 highlighted)
 Revised Consent Form (1 clean, 1 highlighted)
 Revised Research Participant Materials or Questionnaires (1 clean, 1 highlighted)
 Revised Research Staffing Form (1 Clean, 1 highlighted:)
 Part Q(s) for addition of any non-BIDMC personnel

 Change and/or Addition of Study Procedures	 Duration of Subject Participation
 Local Site Enrollment # of Subjects	 Revised and/or New Study Documents or Subject Materials (e.g. diaries, questionnaires)
 Total Enrollment # of Subjects (Multi-Center Trials)	 Investigator Brochure, Date/Version:
 Change in subject selection or subject population	 Change in Remuneration
 Change of Sponsor/Funding	 Research Related Use of Medical Records
 Study Status Change (i.e., CTE, hold, re-open to enrollment)	 Use of Specimens
 Industry Sponsored Protocols only: Sponsor Amendment/Version #:	 Research Related Use of Discarded Material
 Change related to pharmacy or study drug administration	 Revised Sponsor Protocol, Issue Date/Version:
 Addition/Removal of Co-Investigator or Research Staff Member	
For amendments limited to only the addition or removal of research staff in addition to this form the following is required:	

• Research Staffing Form (1 clean, 1 highlighted)• Revised Part E if amendment involves change in Authorized Prescribers for study medication• Part Q and CITI training documentation for any non-BIDMC research staff member.	

AMENDMENT ATTACHMENTS:

 Revised Sponsor Protocol (New Version) (1 clean, 1 highlighted)
 New or Revised Advertisement (1 clean, 1 highlighted)
 Revised Part A (1 clean, 1 highlighted)
 Revised Part B (1 clean, 1 highlighted)
 Revised Consent Form (1 clean, 1 highlighted)
 Revised Research Participant Materials or Questionnaires (1 clean, 1 highlighted)
 Revised Research Staffing Form (1 Clean, 1 highlighted:)
 Part Q(s) for addition of any non-BIDMC personnel
 Revised/New Part E (Obtain pharmacy signature and detail change below)
 Other Revised Part/Form Document (1 Clean, 1 highlighted:)
Specify:

 Revised Sponsor Protocol (New Version) (1 clean, 1 highlighted)
 New or Revised Advertisement (1 clean, 1 highlighted)
 Revised Part A (1 clean, 1 highlighted)
 Revised Part B (1 clean, 1 highlighted)
 Revised Consent Form (1 clean, 1 highlighted)
 Revised Research Participant Materials or Questionnaires (1 clean, 1 highlighted)
 Revised Research Staffing Form (1 Clean, 1 highlighted:)
 Part Q(s) for addition of any non-BIDMC personnel
 Revised/New Part E (Obtain pharmacy signature and detail change below)
 Other Revised Part/Form Document (1 Clean, 1 highlighted:)
Specify:

AMENDMENT DESCRIPTION- REQUIRED FOR ALL SUBMISSIONS

A detailed description of the amendment, in your own words, **MUST** be provided below. The PI may provide a summary of a lengthy sponsor amendment in an attached cover letter or memo, however this should not simply be a copy of the sponsors amendment and/or letter. Either list the current item followed by the new item, or attach a redlined version of the changed document. If the consent form is revised, attach one copy of the consent form in which the changes (including additions and deletions) are clearly highlighted, and one clean copy of the consent form.

Study staff update.

PI Memo/Cover Letter Describing Changes is attached Sponsor Letter Describing Changes is Attached

Impact on Budget/Funding

Does this amendment affect the current budget for the study?
 
 No
 
 Yes, if yes, explain
 
and contact:
 
 - Clinical Trials Office for Industry Funded Studies - Office of Sponsored Programs for Other Funding Sources 	
Does this amendment affect the current funding for the study?
 
 No
 
 Yes, if yes, explain
 
and contact:
 
 - Clinical Trials Office for Industry Funded Studies - Office of Sponsored Programs for Other Funding Sources
---	--

AMENDMENT RATIONALE- REQUIRED FOR ALL SUBMISSIONS

Esmolol to Treat the Hemodynamic Effects of Septic Shock

NCT02369900

December 3, 2020

Statistical Analyses

Preliminary observational data on a cohort of septic shock patients indicated a mean norepinephrine equivalent dose was 0.15 ± 0.09 mcg/kg/min at the 6 hour time point. We anticipated a 33% reduction in mean norepinephrine dose to 0.10 ± 0.09 mcg/kg/min after 6 hours of continuous treatment with esmolol. Based on these estimates, for a two-sample t-test with a power of 80% and a type I error of 0.05, we estimated that a total of 104 patients would be required to show a statistically significant difference between treatment and control groups.

Descriptive statistics are provided for baseline and outcome variables. Continuous variables are presented as means with standard deviations or medians with interquartile ranges (IQR), based on the distribution of the data. Categorical variables are presented as counts with percentages. In univariate analysis, continuous variables were analyzed using a Student's t-test if normally distributed and a Wilcoxon ranked sum test if non-normal. Categorical variables were analyzed using a Fisher's exact test.

The association between continuous infusion of esmolol and need for vasopressor support was assessed by comparing the median 6 hour norepinephrine equivalent dose (NED) between groups using a Wilcoxon rank-sum test. No patients expired prior to 6 hours after enrollment. To analyze the difference in vasopressor dose between groups at 12 hours and over time, we compared NED (recorded hourly for 12 hours) over time between groups using linear mixed effect models accounting for repeated measures and adjusting for pre-intervention NED. The appropriate variance-covariance structure was selected based on Akaike information criterion. Using this model, we tested whether NED was different at 12 hours and for differences in the overall trend over time. A similar analysis was used to assess the difference in heart rate between groups over the first 12 hours and lactate between groups over the first 24 hours; however, in the heart rate analysis, we tested for mean differences at 6 hours, 12 hours and for differences in the overall trend over time, and in the lactate analysis, we used a log-transformed lactate value to test for mean differences at 12 and 24 hours and for differences in the overall trend over time. We compared the median number of shock free days, defined as cessation of all vasopressors during the first 7 days, between the two groups.

To characterize the effects of esmolol infusion on VO_2 , we limited the analysis to patients who were mechanically ventilated during the study period. The VO_2 values were cleaned based on a custom algorithm that eliminated points that met any of the following four criteria: 1) VO_2 value corresponding to a Fraction of Inspired Oxygen (FiO_2) value above 61%. 2) VO_2 value within 10 minutes of a 10-unit change in FiO_2 . 3) VO_2 value above 800 mL/kg/min or below 80 mL/kg/min that is not sustained for at least 30 consecutive minutes. 4) VO_2 value that is 15% higher or lower than the average of the VO_2 values 5 minutes before and after the point in question.

To analyze the difference in oxygen consumption between groups at 12 hours, 24 hours and over time for patients who were on mechanical ventilation at enrollment, we compared VO_2 measurements (standardized by bodyweight in kilograms) over time (recorded every minute

from the time of study drug administration over a period of at least 24 hours) between groups using mixed linear model accounting for repeated measures (n = 15). We did not adjust for pre-intervention VO₂ measurements. Using this model, we tested for mean differences at 12 hours, 24 hours and for differences in the overall trend over time. The appropriate variance-covariance structure was selected based on Akaike information criterion. Additionally, a figure was created by first computing the mean of all the VO₂ observations for a patient by timepoint, and then computing the mean of the means for each timepoint by treatment group.

To characterize effects of esmolol on inflammatory markers in patients with vasopressor-dependent septic shock, we compared log-transformed values of biomarkers at 12 and 24 hours and over time between groups using mixed linear model accounting for repeated measures and adjusting for pre-intervention biomarkers. The appropriate variance-covariance structure was selected based on Akaike information criterion.

In-hospital mortality was compared between groups using the Fisher's Exact test. Baseline covariates appeared to be balanced, so we did not adjust for any additional covariates. Length of hospital and ICU stay was compared between groups using a Wilcoxon ranked sum test and stratified based on hospital survival. To characterize effects of esmolol on SOFA score over the first 24 hours, we compared SOFA at 6, 12, and 24 hours and over time between groups using a mixed linear model accounting for repeated measures and adjusting for pre-intervention SOFA.

All analyses were conducted using Stata 14.2 (College Station, TX) and a p-value of <0.05 was considered significant.

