Consent: If a patient meets all of the inclusion criteria and none of the exclusion criteria, a member of the research team will approach the patient for written informed consent. If the patient is unable to consent, a legally authorized surrogate may be approached per standard IRB procedures. Investigators will explain the study's background and significance, potential risks and benefits, and study protocol. In the event that a physician Investigator or a surrogate is not physically present in the hospital to perform the consent process, a non-physician study staff (research assistant or research coordinator) will coordinate a conference (i.e. FaceTime or Skype video conferencing or telephone) for the physician investigator / surrogate to join in the consent discussion. If consent is obtained, a signed copy will be given to the patient and another copy placed in the medical record. The original signed informed consent will be kept in our locked research office (see specifics in **Section B6 - Recruitment and Consent Procedures**).

Randomization: The randomization will be done in a 1:1 ratio between treatment and control groups in varying blocks of two to six using SAS software. This main list of group assignment will be maintained in the hospital research pharmacy.

Study Arms: After randomization as described above, patients will be assigned to one of the following two arms: esmolol for 24 hours or standard care (no esmolol).

1) Esmolol for 24 hours: Patients in this arm of the study will have Esmolol for 24 hours.

2) "Usual Care": Patients will receive 100 mL of normal saline over 5-10 minutes at the beginning of the study in addition to usual care. When patients are enrolled in a clinical trial there is a time period from consent to study drug administration that depends on the investigative team, the research pharmacy, and the available nursing staff. In order to guarantee that this time interval is similar between the two groups the control arm will receive a small bolus of saline at the beginning of the trial. This will ensure that "time zero" is similar between the two groups.

Blinding: The study will not be blinded as an esmolol infusion must be actively titrated to effect by clinicians and it will noticeably decrease heart rate.

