VO₂ measurements: The Compact Anesthesia Monitor by General Electric is a patient monitor with a built-in module for measuring spirometry and gas exchange. A respiratory therapist will be responsible for connecting/disconnecting the monitor. The gas exchange module measures the volume of inspired gas using a pneumotachograph, and the partial pressure of oxygen with inspiration and expiration using a rapid paramagnetic analyzer. Measurements are taken by a sensor placed in the ventilator tubing and connected to the gas analyzing module,²⁷ providing continuous readings with each patient breath. All data are downloaded onto a laptop used solely for research purposes. The Compact Anesthesia Monitor has been FDA approved for the measurement of VO₂ in

mechanically ventilated patients. The technology has been validated against indirect calorimetry, and is perhaps even more accurate at higher FiO_2 .^{27, 28}

Outcome measures and data management:

Primary endpoint: The primary endpoint will be improvement in the hemodynamic profile as measured by a decrease in the need for norepinephrine support. This will be defined as the difference in norepinephrine dose between groups at 6 hours after onset of study drug.

Justification: The initial trial showed that esmolol not only decreases heart but also decreases vasopressor requirements in patients with septic shock. While the reduction in heart rate might be considered expected from a beta blocker, the reduction in vasopressor dosage is not. However, the reduction in vasopressor dosage would be a significant clinical advancement for the treatment of septic shock and therefore we chose this as the primary clinical endpoint for the trial. We chose the 6 hour time point as the primary endpoint since we anticipate the effect of esmolol will be apparent by that time (rapid onset and effect based on previous study) and that the variance between groups (based on our control preliminary data) is minimal at that time point allowing for adequate power to detect a difference. We also will have secondary endpoints evaluating other time points as well as change over time (below).

Secondary endpoints:

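### The stated 80% power is for a t-test on mean 6-hour dose, but the primary analysis is a Wilcoxon rank-sum test, which does not in general compare medians as the SAP says

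*SAP*

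**What the plan says.** The SAP's sample-size paragraph works in means. The preliminary cohort "indicated a mean norepinephrine equivalent dose was 0.15 ± 0.09 mcg/kg/min at the 6 hour time point". For the other arm it says: "We anticipated a 33% reduction in mean norepinephrine dose to 0.10 ± 0.09 mcg/kg/min after 6 hours of continuous treatment with esmolol". The calculation is "for a two-sample t-test with a power of 80% and a type I error of 0.05", and from it "we estimated that a total of 104 patients would be required". The Protocol (B3, Randomization) allocates 1:1, so 52 per arm.

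The SAP's primary analysis is then described as "comparing the median 6 hour norepinephrine equivalent dose (NED) between groups using a Wilcoxon rank-sum test". No power is given for that test, and no effect estimate with a confidence interval is named for the primary comparison.

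Two other passages bear on the choice. The SAP has a general rule for univariate analysis: "continuous variables were analyzed using a Student's t-test if normally distributed and a Wilcoxon ranked sum test if non-normal". The Protocol (B3, Primary endpoint) says: "This will be defined as the difference in norepinephrine dose between groups at 6 hours after onset of study drug". It names neither the mean nor the median as the summary of that difference.

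**The concern.** Three quantities are in play for one primary comparison. The sample size concerns a difference in means, the SAP's wording promises a difference in medians, and the test responds to neither directly. A rank-sum test responds to the probability that a randomly chosen esmolol patient has a lower dose than a randomly chosen control patient, with ties counted as one half.

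Two things are at stake. The reader is told the trial had 80% power for its primary analysis, but that figure belongs to another test. And a p-value below 0.05 may be reported as a lower median dose when it shows only that doses tend to be lower, for example because more patients have reached zero while the middle of the distribution has not moved.

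**Working it through.** **Inputs (SAP sample-size paragraph; Protocol B3 for allocation).** Means 0.15 and 0.10 mcg/kg/min, SD 0.09 in both arms, alpha 0.05, power 80%, 1:1 allocation. Sidedness is not stated; two-sided is assumed because it reproduces 104.

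**Step 1: reproduce the plan's figure.** Standardised effect = 0.05 / 0.09 = 0.556.
- Normal approximation: n per arm = 2 × (1.960 + 0.842)² × (0.09 / 0.05)² = 2 × 7.85 × 3.24 = 50.9, so 51 per arm and 102 in total.
- Exact (noncentral t): 51.84, so 52 per arm and 104 in total, with power 80.1%.

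The 104 is correct for the t-test.

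**Step 2: Wilcoxon on the same normal inputs.** The test's target is P(esmolol < control) = Φ(0.556 / √2) = Φ(0.393) = 0.653. Its large-sample efficiency against the t-test for normal data is 3/π = 0.955, so n per arm is about 51.84 × π/3 = 54.3. Simulated power is 78.1% at 52 per arm, 79.6% at 54 and 80.3% at 55. So the power is about 2 points below the stated value, and about 55 per arm (110 in total) would be needed for 80%.

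**Step 3: other shapes.** The planning normals put Φ(−0.15/0.09) = 4.8% of control and Φ(−0.10/0.09) = 13.3% of esmolol doses below zero, so they can only be approximate. The documents give means and SDs but no distribution and no share of zero doses, so the shapes below are assumptions. Each row has 52 per arm and two-sided 0.05. Runs of 20,000 have a standard error of about √(0.78 × 0.22 / 20,000) = 0.3 points. All rows except the second keep means 0.15/0.10 and SDs 0.09/0.09.

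| Assumed shape | Wilcoxon power |
|---|---|
| Normal | 78.1% |
| Normal, negatives set to zero, means not re-matched | about 77% |
| Normal censored at zero, means and SDs re-matched | 82.7% |
| Gamma with zeros, 10% control / 30% esmolol | 81.2% |
| Gamma with zeros, 20% / 20% | 85.8% |
| Gamma with zeros, 5% / 15% or 10% / 10% | 89% |
| Gamma | 94.1% |
| Log-normal | 98.0% |

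**Step 4: when the median label holds.** Under a 33% proportional reduction (SD falling from 0.09 to 0.06) the median falls by the same proportion, for example 0.133 to 0.088 for gamma doses. The Wilcoxon has 89% to 95% power. Rejection and a lower median then agree, even though doses are bounded at zero.

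**Step 5: when it fails.** These are constructed cases with equal medians:
- Control doses half uniform on 0.10–0.13 and half on 0.13–0.40; esmolol half on 0–0.13 and half on 0.13–0.16. Both medians are 0.13, P(esmolol lower) = 0.708, and the Wilcoxon rejects 96% of the time.
- 55% of control and 75% of esmolol patients at zero. Both medians are 0, P(esmolol lower) = 0.608, and it rejects 63% of the time.
- Gamma doses with median 0.132 in both arms, with half of the below-median esmolol patients moved to zero: it rejects about 19% of the time.

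Scaling every below-median dose by 0.4, or setting all of them to zero, gives about 45% and 60%. Those two cases leave a gap just below 0.132, so the altered arm's median is not unique, and I do not rely on them.

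A difference in spread alone need not mislead. With log-normal doses, equal medians of 0.13 and log-scale SDs of 0.3 and 0.9, P is 0.500 and rejection is 6.5%.

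**Step 6: not a test of means either.** With gamma doses, equal means of 0.10 and SDs of 0.09 and 0.03, the Wilcoxon rejects 44% of the time and the t-test 6%. So the power of a test on means does not simply carry over.

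**The case against.** The strongest reply is that this is a matter of wording. The SAP's general rule allows a Wilcoxon test for non-normal continuous variables. The Protocol's endpoint is a difference in dose without a named summary. The 104 reproduces. In the equal-median examples doses really are lower with esmolol: in the first, the mean falls from 0.190 to 0.105. Rejecting there is right for the Protocol's endpoint, and only the word median would be wrong. The examples are also built so that the medians stay equal. All of this stands, and it limits the point to the label, the conclusion and the quoted power.

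It is also fair that restating power changes no decision once data are analysed. It remains a correction to what the SAP tells its reader about the primary test.

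Four stronger readings are tempting, and the documents do not support them:
- **That 104 is too few.** The lowest power found is about 77%, and most shapes that respect zero give more than 80%.
- **That the zero bound itself defeats the median reading.** It does not; a proportional reduction respects zero and keeps the label valid. What matters is a difference in shape or in the share of zeros.
- **That the Wilcoxon was chosen after seeing the data.** The SAP is written in the past tense and contains observed facts, but these do not date the choice of test.
- **That choosing the test from the data inflates type I error.** The SAP's rule selects on normality, not on the smaller p-value. Simulated, that rule gave 4.4% to 5.5%, close to nominal.

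**Conclusion.** The point holds as one of labelling and stated power. The 80% is for a t-test on means. The primary test is a rank-sum test, with about 78% power on the plan's own normal inputs and about 77% to 98% over the shapes tried. A significant result supports the statement that 6-hour doses tend to be lower with esmolol. It supports a lower median only if the arms differ by something close to a shift or a proportional reduction, which the plan neither assumes nor proposes to check.

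The 78% rests on normal doses with a common SD of 0.09 and two-sided testing. The rest of the range rests on assumed shapes, and the equal-median rejection rates show what is possible, not what is expected. The correction is worth making because it concerns the primary comparison and costs almost nothing.

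**What to change.** 1. In the sample-size paragraph, keep 104 and the t-test derivation, and add that the primary Wilcoxon test has about 78% power on the same inputs with 52 per arm, and roughly 77% to 98% over zero-bounded or skewed shapes, with those shapes stated as assumptions.
2. In the primary analysis, replace the description of the test as a comparison of medians. Suggested text: *The Wilcoxon rank-sum test will assess whether norepinephrine equivalent doses at 6 hours tend to be lower with esmolol than with usual care.* Word the conclusion the same way. Medians with IQR can stay as description.
3. Name one matching effect measure with a 95% confidence interval: either the Hodges-Lehmann shift or the probability that an esmolol patient has the lower dose, with ties counted as one half. The probability is easier to interpret if many doses are zero.
4. Show the difference in means, on which the trial was sized, with its 95% confidence interval as a labelled secondary check and not as a second primary test.

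Cost: wording in the SAP and report, one extra estimate beside the primary effect measure, and a stated power about 2 points lower on the plan's own inputs. No new data are needed, and neither the sample size nor the primary test changes.
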